Title: FitEx for Endometrial Cancer Survivors: Initial Efficacy

NCT trial number: NCT05737745

November 22, 2024

Study Protocol:

Overview:

This study targets 30 endometrial cancer survivors (ECS) and 2-5 support team members per ECS enrolled in intervention groups. We will use a 3-group design [FitEx (intervention 1) versus FitEx+yoga (intervention 2) versus standard-of-care (control)] with 3 assessments (pre, post [after 8-week program], and follow-up [6-month]). All participants will be given the option to receive a Fitbit Charge 5™ to objectively measure moderate-vigorous physical activity. ECS randomized to either intervention arm will participate in the 8-week FitEx program with their support team members which includes goal setting, self-monitoring, and weekly 30-minute synchronous sessions via Zoom. ECS in the control group will receive a one-time educational newsletter and will not recruit support team members. This protocol will be completed twice, once in 2023 and once in 2024.

OBJECTIVES:

- Aim 1: Among ECS, compare changes in objective MVPA between intervention groups and usual care (FitEx vs. control and FitEx+yoga vs. control) at 8 weeks.
- Aim 2: Among ECS, compare secondary efficacy outcomes and maintenance.
 - Aim 2a: Examine changes in secondary efficacy outcomes [e.g., quality of life (QOL), self-compassion, flourishing, self-efficacy, social support, habituation of exercise, and fruit/vegetable consumption] between intervention and usual care conditions (FitEx versus control and FitEx+yoga versus control) at 8 weeks.
 - Aim 2b: Explore maintenance of MPVA and secondary outcomes between intervention versus usual care (FitEx vs. control and FitEx+yoga vs. control) at 6 months.
- Aim 3: Among support team members, compare changes in MVPA and secondary outcomes (listed above) between intervention groups (FitEx vs. FitEx+yoga) at 8 weeks and 6 months.

RECRUITMENT:

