If an ECS is interested in participating, research study personnel will conduct a screening assessment and informed consent process either in-person or virtually. If conducted in-person, the informed consent process documents will be stored in the study coordinator’s office at Carilion Clinic. If conducted virtually, the informed consent process will be documented within REDCap. Participants may be consented on REDCap either over the phone or via teleconference depending on their preference. Consents conducted via teleconference will use secure, password protected Microsoft Teams or WebEx platforms. Zoom will not be used to consent participants. Support team members will undergo the same consent process as ECS after follow-up call and screening. All participants will be provided ample time to decide if they would like to join the study. There will be multiple opportunities for the participant to opt out before enrollment. Prior to consent, all potential participants will be sent a copy of the consent form for their review. A phone call or secure, web-based teleconference will be scheduled for interested participants to fill out the econsent via REDCap.

RANDOMIZATION & GROUPS

Each ECS who enrolls in the study will be randomized into one of three groups:

1. Standard-of-care (control)
2. FitEx intervention (FitEx-ECS)
3. FitEx intervention with integrated yoga principles (FitEx-ECS+yoga)

Overall, this study targets 10 ECS per group (30 total ECS) with 2-5 support team members per ECS in each intervention group (approximately 30 total support team members in each intervention group) yearly, for 2 years (90 participants per year, 180 participants total). All participants will be given the option to receive a Fitbit Charge 5™ to objectively measure moderate-vigorous physical activity.

Control Group:

ECS in the control group will be given the option to receive a Fitbit and will be sent a one-time educational newsletter about survivorship PA and nutrition recommendations. Control group participants will fill out all questionnaires at baseline, post, and 6-months follow up. Control

group participants will not recruit support team members, fill out FitEx-specific forms, nor participate in weekly Zoom sessions.

Intervention Groups:

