Due to the small sample size and exploratory nature of this pilot study, statistical analyses will be descriptive rather than inferential. However, we will determine if a signal exists between intervention and control groups regarding participants' physical activity using MET (metabolic equivalents) data from Fitbits. Weekly data will be compared at week-8 (intervention conclusion) to baseline. Data is considered appropriate if it was collected from at least 4 days per week. Data from missing days was input at "0". Students T-tests were used to compare means from each intervention group to the control condition for the primary outcome.

Attendance/Retention Measures

Participants who enroll in the study will be asked to attend weekly meetings. The attendance at the meetings will be recorded to assess the percentage of participants who are interested in weekly meetings. The acceptability of FitEx will be assessed in part using meeting attendance. Attendance and retention will be used as measures of intervention acceptability.

The number of support group members who attend each session will also be noted. The ratio of support group members to endometrial cancer survivor participants will also be noted.

We will examine our attrition rate and attendance as noted above. We will also reach out to participants who do not complete our study to determine the reasons for their decisions. Our study will be feasible in its current state if our attrition rate is between 10-27%.

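### Entering missing Fitbit days as 0 scores unobserved days as inactive, so the primary comparison mixes activity with the number of days recorded

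*Combined protocol and SAP*

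**What the plan says.** Aim 1 (Objectives) is to "compare changes in objective MVPA between intervention groups and usual care" at 8 weeks. The analysis is set out under Statistical Assessment: Measures. It looks for a signal in "physical activity using MET (metabolic equivalents) data from Fitbits", with this time contrast: "Weekly data will be compared at week-8 (intervention conclusion) to baseline". The rule for incomplete weeks is "Data is considered appropriate if it was collected from at least 4 days per week. Data from missing days was input at" zero. The test is then given: "Students T-tests were used to compare means from each intervention group to the control condition for the primary outcome".

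No other section changes the zero rule. The plan does not define non-wear, does not use a mean per recorded day and has no sensitivity analysis for missing days. It does not say outright that weeks with fewer than 4 days are excluded, or whether the t-test is on change from baseline or on week-8 means.

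**The concern.** A day on which the device was not worn or not synced is unobserved; it is not a day without activity. The plan itself foresees such days: the sync reminder asks participants to upload the past week's activity, so an unsynced day may well contain some. The 4-day threshold treats four days as enough to represent a week, yet the zero rule scores that week at 4/7 of its recorded daily rate. If the outcome is all-day METs, as the Measures text allows, zero is not a possible value for a living participant.

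The rule feeds the primary t-tests and the signal that the pilot is meant to detect. A reader of the results could not tell a difference in activity from a difference in days recorded.

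Several features are the same in all arms: the device offer, the sync reminders and the 6-month wear payment (which does not bear on week 8). Contact is not the same. Only the intervention arms have weekly sessions, weekly newsletters and self-monitoring, although the self-monitoring can be done on a log outside the portal. For controls the plan says "group participants will not recruit support team members, fill out FitEx-specific forms, nor participate in weekly Zoom sessions". Unequal recording is therefore plausible, but nothing in the documents shows it or its direction.

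**Working it through.** **Inputs from the document.** At least 4 of 7 days; missing days set to 0; Student's t-test of each intervention arm against control; sample size "Overall, this study targets 10 ECS per group (30 total ECS") per year for two years, so 10 per arm in one yearly cohort and 20 over both. The accrual arithmetic agrees with the plan: (3 × 10 + 2 × 30) × 2 = 180. There is no stated alpha, power, SD, mean or wear, so there is no other figure to reproduce.

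**1. Understatement of one accepted week.** Let d be the days recorded and f the activity on missing days relative to recorded days. Understatement = 1 − d / (d + (7 − d)f).

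| f | d = 6 | d = 5 | d = 4 |
|---|---|---|---|
| 1 | 14% | 29% | 43% |
| 0.5 | 8% | 17% | 27% |
| 0.25 | 4% | 9% | 16% |
| 0 | 0 | 0 | 0 |

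This step depends only on the rule and f. It takes weeks under 4 days as excluded; if they are kept and zero-filled, the understatement is larger.

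**Assumptions for steps 2 to 5 (not from the document).** Outcome in MVPA minutes; activity m = 10 to 30 min/day; SD of change 67 to 126 min/week; equal recorded days at baseline; a two-sided 5% benchmark; and f = 1 unless stated.

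**2. Equal recorded days in both arms.** A true effect shrinks to about d/7 of its size. An assumed +52 min/week at 5.8 days is estimated as 52 × 5.8/7 = +43. In simulation (20,000 trials per scenario), with days falling equally from 6.7 to 5.8, the false-positive rate was 4.8–5.2%.

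**3. No true effect, unequal days at week 8 only.** False difference = f × m × gap in days. A one-day gap at f = 1 gives 10 to 30 min/week. SE = SD × √(2/n), which is 30.0 to 56.3 at n = 10 and 21.2 to 39.8 at n = 20. The false difference is therefore about 0.2 to 1.0 SE and 0.25 to 1.4 SE. Rejection rates from the noncentral t distribution:

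| Per arm | One-day gap, f = 1 | Half-day gap at f = 1, or one-day gap at f = 0.5 |
|---|---|---|
| 10 | 5.3–15.8% | 5.1–7.6% |
| 20 | 5.7–28.2% | 5.2–10.6% |

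The top of each range pairs 30 min/day with SD 67. At 10 min/day and a one-day gap the rates are 5.3–6.2% (n = 10) and 5.7–7.5% (n = 20). With 27% attrition, the upper end of the plan's feasibility range, 10 × 0.73 = 7.3 and 20 × 0.73 = 14.6. The one-day-gap rates are then 5.2–12.1% (n = 7) and 5.5–22.0% (n = 15).

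Simulation of the one-day gap (6.5 against 5.5 days at week 8) gave 5.5–15.3% (n = 10) and 6.0–27.2% (n = 20). The recorded-day mean on the same data gave 4.6–5.3%, with missing days unrelated to activity.

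**4. The same one-day gap at baseline and week 8, change scores.** With stable activity the false difference is 0 and the simulated rate is 5.1–5.2% (n = 20). If both arms rise by 20 min/week, the bias is 20 × 1/7 = 2.9 min/week. If only week-8 means are compared, the gap at week 8 biases the result regardless of baseline.

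**5. True +52 min/week with a one-day gap at week 8 (5.5 against 6.5 days).**

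- Intervention arm records fewer days: (7m + 52) × 5.5/7 − 6.5m = +31, +21, +11 at m = 10, 20, 30.
- Intervention arm records more days: (7m + 52) × 6.5/7 − 5.5m = +58, +68, +78.
- Reversal, with control at 6.5 days: the estimate is zero when the intervention arm records 6.5 × 7m/(7m + 52) days. That is 5.21 at m = 30 (gap 1.29), 4.74 at m = 20 (gap 1.76) and 3.73 at m = 10. The last is below the 4-day minimum, so reversal cannot occur there if shorter weeks are excluded.

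**6. A second set of assumptions.** Take activity on a relative scale with within-person daily CV 0.5, between-person CV 0.2 to 0.5, 6 recorded days at baseline in both arms, and 6.5 against 5 days at week 8. The simulated false-positive rate on change is then 29–34% (n = 10) and 54–61% (n = 20). If the intervention arm has the 5 days, a true +20% appears as about −7%. The error rate depends strongly on the assumed gap and variability.

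**The case against.** The strongest reply is that only step 1 follows from the plan. The means, SDs, wear levels and the +52 effect are all assumed, and the highest error rates combine the most active participants with the smallest SD and with missing days as active as recorded ones. At f = 0.5 the false difference halves. At f = 0 it vanishes, and the recorded-day mean becomes the biased rule. The illustrations are in MVPA minutes, while the Measures text names METs, so the rates do not carry over directly. The analysis is labelled descriptive and sets no alpha, the reminders go to all groups and should recover some unsynced days, and under equal wear the rule only dilutes.

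Much of this stands. The arm-level figures are illustrations, they need f to be stated, and they do not show that this trial's result is biased in a given direction. Optional recording at baseline is also weak evidence about gaps within an accepted week, since it bears first on whether a participant records at all.

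It does not rescue the rule. The zeros are wrong for any participant whose missing days were not truly inactive. The bias is in the arm means, so descriptive summaries carry it too. Dilution alone matters in a pilot that looks for a signal.

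**Conclusion.** The concern holds, and the zero rule must be changed. As written, the primary outcome is activity per recorded day multiplied by days recorded. The firm part is the understatement of individual weeks: up to 43% in a 4-day week if missing days resemble recorded days, and nil only if every missing day was inactive.

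The effect on the arm comparison is conditional. With recorded days equal between arms it is dilution without extra false positives. With change scores, a false difference needs the change in recorded days to differ between arms, or a common shift in activity on top of a constant gap. With week-8 means, a gap at week 8 is enough. Under the MVPA assumptions above, a one-day gap gives a false difference of 10 to 30 min/week at f = 1 and 5 to 15 at f = 0.5. Confidence is high that the rule is wrong; whether it biases the arm contrast materially here cannot be settled without the wear data.

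**What to change.** - Replace the zero rule. For weeks with at least 4 recorded days, use the mean over recorded days (or that mean × 7). State that weeks with fewer days are treated as missing.
- State whether the t-test is on change from baseline or on week-8 means, and whether the outcome is METs or MVPA.
- Report recorded days by arm at baseline and at week 8.
- State the assumption that missing days are unrelated to activity. Test it with a sensitivity analysis that gives missing days 0, 0.5 and 1 times the participant's own recorded-day mean; the present rule is the first case.
- The Measures text is partly in the past tense, which suggests that the zero-filled analysis may already have been run. If so, report both derivations, and disclose and date the change.

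The cost is SAP wording, a re-run of the derivation on existing daily data and one short table. If results exist, it is also a disclosed post-hoc change to the primary derivation.

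The replacement has its own error. Over a week the zero rule is wrong by (7 − d)fm and the recorded-day mean by (7 − d)(1 − f)m. These are equal at f = 0.5, so the recorded-day mean is worse only if missing days average less than half of recorded-day activity. The documents cannot settle f, which is why the sensitivity table is needed.

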After enrollment: All participants will have the option to receive Fitbit Charge 5TMs to track their data over the course of the study and for them to keep after the study. If a participant already owns a Fitbit they wish to use, they will instead be reimbursed \$99 for using their personal Fitbit for the study.

Post-intervention: Upon completion of the post-program exit interviews, participants in the intervention groups will receive \$10.

At 6-months follow-up: Upon completion of both filling out the program survey and wearing their Fitbit for one week at the 6-months follow-up timepoint, all participants (from any of the three groups) will be compensated \$20.

ASSESSMENTS

All participants will be assessed at baseline (week 1), post-program (week 9), and follow-up (6 months).

Pre-program:

At baseline, participants in all three groups will have the option to record Fitbit data for 7 days. Participants in the intervention groups will also be asked to track self-monitored physical activity, track self-monitored fruit and vegetables intake, and fill out the FitEx pre-program form. All participants will receive questionnaires. Questionnaires will be distributed via REDCap at baseline, post, and follow up.

Program:

During the 8-week duration of intervention program, Fitbit data will be collected from all participants in the control, FitEx-ECS, and FitEx-ECS+yoga groups.

In both intervention groups, self-monitored physical activity and fruit and vegetables intake will be tracked with the FitEx-ECS portal within Fitabase or with the FitEx Individual Log (see attached). Intervention group-specific weekly newsletters and Zoom sessions will occur throughout the duration of the 8 weeks. Intervention participants will be verbally reminded of the audio recording at the beginning of each Zoom session.

Additionally, a video of each session's synchronous movement will be recorded by the instructor only so that participants in either intervention group who were unable to attend can participate in the physical movement when their schedule allows.

Post-program:

After the 8-week program, participants in both intervention groups will fill out the FitEx post-program form and participants in all groups will repeat questionnaires, all distributed via REDCap. For both intervention groups, 30- to 45-minute semi-structured interviews will be scheduled and conducted with ECS survivors and support team members (See "Follow Up Materials" attachment for interview guide.)

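### The primary t-tests use no baseline covariate; pairwise adjustment for baseline activity would give a small, nearly free gain in precision at low to moderate baseline-to-week-8 correlation

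*Combined protocol and SAP*

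**What the plan says.** Under Statistical Assessment, Measures, the plan states that "statistical analyses will be descriptive rather than inferential", but it also undertakes to decide whether a signal exists between intervention and control in Fitbit-measured activity. The tool is given in one sentence: "Students T-tests were used to compare means from each intervention group to the control condition for the primary outcome". Just before it the plan says "Weekly data will be compared at week-8 (intervention conclusion) to baseline", and Aim 1 (Objectives) is to "compare changes in objective MVPA between intervention groups and usual care" at 8 weeks. Together these point to t-tests on change scores, but the sentence that names the test does not say so.

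On the data available, the Pre-program text under Assessments says that "participants in all three groups will have the option to record Fitbit data for 7 days". Baseline activity is therefore sought in every arm, but recording it is optional.

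On size, Randomization & Groups gives 10 endometrial cancer survivors per group per yearly run. The Overview adds: "This protocol will be completed twice, once in 2023 and once in 2024". The plan does not say whether the two runs will be pooled. It treats attrition of 10-27% as feasible (Attendance/Retention Measures). It states no alpha, power, effect size, SD or baseline-to-week-8 correlation.

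**The concern.** A t-test on change fixes the coefficient of baseline at 1, and a t-test on week-8 means fixes it at 0. ANCOVA estimates that coefficient from the data. When the correlation is moderate, neither fixed value is close to the best one, and part of any chance baseline difference between arms is carried into the estimated effect. That is how precision is lost; it is not a separate bias.

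What is at stake is the width of the interval around the signal. With about 10 survivors per arm, a 95% interval reaches most of an SD either side of the estimate. A narrower interval from the same two measurements is worth having in a pilot whose product is an estimate.

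**Working it through.** **Inputs.** From the documents: two pairwise comparisons with control; n = 10 per arm in one run; n = 20 if both runs are pooled; 10 × 0.90 = 9 and 10 × 0.73 = 7.3 per arm after the stated attrition range. Assumed: r from 0.3 to 0.9, equal SDs at both times and in all arms (set to 1), normal data, complete baseline weeks. The plan has no power or precision figure to reproduce.

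**Variance of the estimated difference, two arms of n:**
- week-8 means: 2/n
- change scores: (2/n) × 2(1 − r)
- two-arm ANCOVA: (2/n) × (1 − r²) × [1 + 1/(2n − 4)]; the last factor is the small-sample cost of chance baseline imbalance

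The interval uses t on 2n − 2 df for the t-tests and 2n − 3 df for ANCOVA.

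**Worked case, n = 10, r = 0.5.** Change: 0.2 × 1 = 0.200, SE 0.447, times t(18) = 2.101, half-width 0.940. ANCOVA: 0.2 × 0.75 × 1.0625 = 0.159, SE 0.399, times t(17) = 2.110, half-width 0.842. The ratio is 0.896, so the interval is about 10% narrower. When the SE is estimated from the sample, mean half-widths are slightly smaller (0.927 and 0.829), with almost the same ratio.

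**Mean 95% half-widths in SD units (change t-test → two-arm ANCOVA).** They agree with a simulation of 20,000 trials per cell to within about 0.002, with simulated coverage of 94.7-95.3%.

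| r | n = 7 | n = 10 | n = 20 |
|---|---|---|---|
| 0.3 | 1.350 → 1.148 (−15%) | 1.096 → 0.913 (−17%) | 0.752 → 0.615 (−18%) |
| 0.5 | 1.141 → 1.042 (−9%) | 0.927 → 0.829 (−10%) | 0.636 → 0.559 (−12%) |
| 0.7 | 0.884 → 0.859 (−3%) | 0.718 → 0.684 (−5%) | 0.493 → 0.461 (−6%) |
| 0.8 | 0.721 → 0.722 (0%) | 0.586 → 0.574 (−2%) | 0.402 → 0.387 (−4%) |
| 0.9 | 0.510 → 0.525 (+3%) | 0.414 → 0.417 (+1%) | 0.284 → 0.281 (−1%) |

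**Break-even on interval width against change scores:** r of about 0.80 at 7 per arm, 0.87 at 10 and 0.94 at 20. Above these values the change-score interval is narrower.

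**If week-8 means are tested instead.** At 10 per arm the t-test half-width is 0.927 whatever r is. ANCOVA is narrower above r of about 0.25. The gain at r = 0.5 is again about 10%, and at r = 0.1 ANCOVA is about 3% wider (0.953).

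**Missing baseline weeks.** A change score already needs a baseline, so adjustment loses nobody further. A week-8 test does not need one. At r = 0.5, if adjustment cuts the analysed number from 10 to 8 per arm, the ANCOVA half-width is 0.95 against 0.93 for the t-test on all 10, and the gain becomes a slight loss.

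**Skewed data.** With lognormal activity (log-SD 0.7), n = 10 and r = 0.25/0.44/0.65/0.76, half-widths were 1.09/0.94/0.74/0.61 for change and 0.86/0.79/0.65/0.55 for two-arm ANCOVA, with coverage of 95.5-95.9%. The gain does not depend on normality.

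**The case against.** The strongest reply is that nothing here is wrong. The plan calls itself descriptive, sets no precision target, and already compares week 8 with baseline. On that reading the point is only a preference for ANCOVA over change scores, and its benefit rests on a correlation that nobody has stated. At the 7 to 9 per arm that the plan's own attrition range implies, the gain is smaller, and it disappears at high r. Most of this stands. It limits the size of the point but does not remove the gain at low to moderate r.

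Two further objections also stand. The adjustment is nearly free only where baseline weeks exist, and recording them is optional. And a single three-arm model, although slightly narrower when variances are equal (0.80 at n = 10, r = 0.5), is less robust. If the other intervention arm's residual SD is 0.5 or 1.5 times the rest, its coverage becomes 91.5% or 97.8%, and in the second case its half-width (0.96) exceeds that of the change t-test (0.93). Pairwise ANCOVA stays at 95% with 0.83. The remedy should therefore be pairwise.

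A reader might infer that the t-tests are biased or invalid, or that baseline is ignored. The documents support neither. Randomisation protects both forms of the t-test, and Aim 1 and the Measures text both bring baseline in.

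**Conclusion.** The point holds as a minor improvement. The planned comparison is valid but, at low to moderate correlation, less precise than it could be with measurements the study already seeks. Against change scores at 10 per arm the interval narrows by roughly 5-17% for r between 0.3 and 0.7. The gain is about 2% at r = 0.8 and turns into a loss of about 1% at r = 0.9. At 7 per arm it has gone by r = 0.8.

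These figures assume r, equal SDs and complete baseline weeks. They do not model the setting of missing days to zero, which may itself alter r. It would be wrong to infer that the sample size or power is in error, since the plan states no power basis, or that adjustment is better at every r.

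**What to change.** 1. State whether the t-tests use change from baseline or week-8 means.
2. For each intervention arm against control, fit week-8 activity on arm and baseline activity (pairwise ANCOVA), adding year if the two runs are pooled. Report the adjusted difference with its 95% interval.
3. Offer a three-arm model only if a common variance across arms is accepted in advance.
4. Report how many survivors in each arm have both a baseline and a week-8 week, and confirm that the baseline week precedes any intervention exposure. The Assessments section heads it as pre-program but also labels it week 1.
5. The Measures text is partly in the past tense. If the t-tests have already been run, keep them and put the adjusted differences beside them, labelled post hoc.

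The cost is one degree of freedom per comparison (one more for year if pooled) and a few lines of code. If week-8 means would otherwise be tested, it also costs any survivors who have no baseline week. The adjustment does not repair the zero-filling of missing days, which needs its own answer.

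### Minor: naming Welch's t-test instead of Student's would protect the primary comparisons if analysed group sizes and variances both differ

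*Combined protocol and SAP*

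**What the plan says.** All references are to the combined protocol and SAP.

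- **Test** (Statistical Assessment, Measures): "Students T-tests were used to compare means from each intervention group to the control condition for the primary outcome". Neither pooling nor an unequal-variance version is mentioned. Fitbit MET data at week 8 are compared with baseline. The same paragraph calls the analyses descriptive and not inferential, but then says that the comparison will establish whether there is a signal.
- **Group size** (Randomization & Groups): "this study targets 10 ECS per group (30 total ECS"), "yearly, for 2 years (90 participants per year, 180 participants total").
- **Device data** (Assessments, Pre-program): "participants in all three groups will have the option to record Fitbit data for 7 days". The device itself is also optional.
- **Valid week** (Measures): "Data is considered appropriate if it was collected from at least 4 days per week". Missing days are entered as zero. The text does not say what happens to a week with fewer than 4 days.
- **Attrition** (Attendance/Retention Measures): "Our study will be feasible in its current state if our attrition rate is between 10-27" per cent.

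No significance level, sidedness, power, SD or decision rule is given.

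**The concern.** Student's test estimates one common variance, weighted by each group's degrees of freedom. With equal group sizes, unequal variances do little harm. With unequal sizes, the larger group dominates the pooled variance. If the smaller group is the more variable, the standard error is then too small and the interval too narrow. If the larger group is the more variable, the reverse holds.

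Both conditions are plausible here. Loss of data may differ between arms, because intervention survivors self-monitor and are encouraged to attend weekly sessions while controls receive one newsletter. Attendance is voluntary, so the intervention actually received will vary among intervention survivors. Zero-filling of missing days could add to a variance difference if device wear differs by arm. At stake is whether the reported precision of the two primary comparisons can be taken at face value.

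**Working it through.** **Step 1. The plan's own head count.** Three groups of 10 survivors plus two intervention groups with about 30 support members each: 3 × 10 + 2 × 30 = 90 per year, and 2 × 90 = 180. This reproduces the stated totals. The primary comparison therefore starts from 10 survivors per group in one cycle, or 20 if the two cycles are pooled.

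**Step 2. Analysed sizes under the stated attrition.** 10 × 0.90 = 9.0 and 10 × 0.73 = 7.3; 20 × 0.90 = 18.0 and 20 × 0.73 = 14.6. I use 7 and 9 for one cycle, and 15 and 18 for two.

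**Step 3. How likely are unequal sizes?** If each survivor is retained independently with probability q in both groups, the probability of unequal sizes is 1 − Σ b(k)², where b(k) is the binomial probability of retaining k survivors.

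| Start per group | q = 0.90 | q = 0.73 |
|---|---|---|
| 10 | 1 − 0.313 = 69% | 1 − 0.200 = 80% |
| 20 | 1 − 0.214 = 79% | 1 − 0.142 = 86% |

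This uses attrition alone. A gap of 3 or more has probability 6% to 20% with 10 per group, and 18% to 37% with 20.

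**Step 4. Direction of the error.** Set the control variance to 1 and the intervention variance to r². On average the pooled squared standard error is

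[((n₁ − 1)r² + (n₀ − 1)) / (n₁ + n₀ − 2)] × (1/n₁ + 1/n₀),

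while the true value is r²/n₁ + 1/n₀. With r = 2:

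- Intervention 7, control 9: pooled (6 × 4 + 8)/14 × (1/7 + 1/9) = 0.581; true 4/7 + 1/9 = 0.683. Ratio of standard errors √(0.581/0.683) = 0.92, about 8% too small.
- Intervention 9, control 7: pooled (8 × 4 + 6)/14 × (1/9 + 1/7) = 0.689; true 4/9 + 1/7 = 0.587. Ratio √(0.689/0.587) = 1.08, about 8% too large.

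**Step 5. Error rates.** Simulated normal change scores with no mean difference, 200,000 replicates per setting. Assumed: two-sided 5% level, intervention SD 1.5 or 2 times control. Welch's statistic is the mean difference divided by √(s₁²/n₁ + s₀²/n₀), with Satterthwaite degrees of freedom. Each cell shows SD ratio 1.5 / 2. Simulation error is about 0.1 percentage point.

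| Intervention v control | Student | Welch |
|---|---|---|
| 7 v 9 | 6.4% / 7.6% | 5.0% / 5.1% |
| 15 v 18 | 5.9% / 6.7% | 5.0% / 5.0% |
| 9 v 7 | 4.2% / 4.0% | 4.8% / 4.9% |
| 18 v 15 | 4.4% / 4.1% | 5.0% / 5.0% |
| 10 v 10 | 5.2% / 5.6% | 4.9% / 5.1% |

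With equal variances, Student's test gave 5.0% at all these sizes.

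**Step 6. Averaged over random retention, 10 per group.** Same retention in both groups (90% or 73%): Student 5.2% to 5.4% at ratio 1.5, and 5.5% to 5.8% at ratio 2. Intervention 73% and control 90%: 6.3% / 7.5%. Intervention 90% and control 73%: 4.4% / 4.3%.

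**The case against.** The strongest objection is that the plan declares no error rate that could be breached. It calls its analyses descriptive and states no significance level, so the 5% used here is mine. That stands, and it keeps the point minor. It does not remove the point: the plan names this test as its means of finding a signal, and the same pooled standard error would underlie any interval reported.

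Three stronger readings are tempting, and the documents do not support them.

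- *The plan inflates false positives.* Inflation needs two things together: a more variable intervention group and heavier loss from that group. The documents establish neither. If control is the smaller group, the test is conservative; if expected retention is the same, the average rate is close to 5%. A rate near 12% appears only with strong differential loss, such as 5 v 10 at SD ratio 2 (11.8%), which means half the intervention group gone. Optional device use could cause that, but the documents give no rate for it.
- *The plan's rules must leave unequal groups.* With 10 per group and random loss, sizes are equal 20% to 31% of the time. The plan does not say that weeks under 4 days are excluded, and its Program section expects Fitbit data from all participants during the 8 weeks.
- *The plan explicitly assumes equal variances.* It only names Student's test. Pooling follows from the usual definition, and the wording may be loose.

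**Conclusion.** The point holds as a cheap improvement. The only test named for the primary comparisons pools the variances, in a design where unequal analysed sizes are likely. Within the stated attrition range the departure from an assumed 5% is up to about 2.6 percentage points upwards (7.6% at 7 v 9) and about 1 point downwards (4.0% at 9 v 7), so its direction cannot be predicted from the documents. These figures rest on an assumed two-sided 5% level, assumed SD ratios of 1.5 to 2 and normally distributed changes. If either the sizes or the variances turn out equal, the choice of test makes almost no difference.

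**What to change.** In Statistical Assessment, Measures, replace Student's t-test with Welch's unequal-variance t-test, and report the mean difference with its Welch confidence interval, for FitEx versus control and for FitEx+yoga versus control. State in the same place how weeks with fewer than 4 days and survivors without Fitbit data are handled, so that the analysed group sizes are defined.

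Cost: when the variances are equal, Welch's test gives up some degrees of freedom, for example from 18 to 16.5 on average at 10 v 10. For a true difference of 1 SD, power goes from 56.3% to 55.7% at 10 v 10 and from about 45.6% to 44.4% at 7 v 9, a loss of about 1 percentage point. The plan describes this test in the past tense, so if the analysis has already been run, it must be rerun.
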